9.0 Ancillary Treatment/Supportive Care

- 9.1 Antiemetic's may be used at the discretion of the attending physician.
- 9.2 Blood products and growth factors should be utilized as clinically warranted and

^b If primary cause is due to lymphoma, dose delay or reduction may not be needed.

following institutional policies and recommendations. The use of growth factors should follow published guidelines of the American Society of Clinical Oncology (ASCO), Recommendations for the Use of WBC Growth Factors: American Society of Clinical Oncology Clinical Practice Guideline Update. J Clin Oncol 2015;33:3199-3212.

- 9.3 Patients should receive full supportive care while on this study. This includes blood product support, antibiotic treatment, and treatment of other newly diagnosed or concurrent medical conditions. All blood products and concomitant medications such as antidiarrheals, analgesics, and/or antiemetics received from the first day of study treatment administration until 30 days after the final dose will be recorded in the medical records.
- 9.4 Diarrhea: This could be managed conservatively with loperamide. The recommended dose of loperamide is 4 mg at first onset, followed by 2 mg every 2-4 hours until diarrhea free (maximum 16 mg/day).

In the event of grade 3 or 4 diarrhea, the following supportive measures are allowed: hydration, octreotide, and antidiarrheals.

If diarrhea is severe (requiring intravenous rehydration) and/or associated with fever or severe neutropenia (grade 3 or 4), broad-spectrum antibiotics must be prescribed. Patients with severe diarrhea or any diarrhea associated with severe nausea or vomiting should be hospitalized for intravenous hydration and correction of electrolyte imbalances.

- 9.5 Carriers of hepatitis B virus (HBV) should be closely monitored for clinical and laboratory signs of active HBV infection and for signs of hepatitis during and for up to several months following Rituxan therapy. In patients who develop viral hepatitis, Rituxan and any concomitant chemotherapy should be discontinued and appropriate treatment, including antiviral therapy, initiated. There are insufficient data regarding the safety of resuming Rituxan therapy in patients who develop hepatitis subsequent to HBV reactivation.
- 9.6 Prohibited Medications or Therapies
 - 9.61 CYP3A Inhibitors/Inducers

Treatment with strong and moderate inhibitors or inducers of CYP3A is not allowed during this trial. See Appendix I for more information. In addition, grapefruit or grapefruit products, Seville organs or products from Seville organs, and Star fruit should be avoided for the duration of the trial due to their effect on CYP3A4.

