Metabolism: Biotransformation of venetoclax in humans primarily involves enzymatic oxidation on the dimethyl cyclohexenyl moiety to form metabolites. One of the metabolites, M5, undergoes CYP- mediated cyclization at the α -carbon of piperazine to generate M27. In human, M27 was identified as a major metabolite with an inhibitory activity against BCL-2 that is at least 58-fold lower than venetoclax *in vitro*.

Half-life elimination: 17-41 hours following a single dose of venetoclax **Excretion:** Venetoclax is primarily eliminated as metabolites in feces (99.9 \pm 5.0%) with negligible renal elimination (< 0.1%). Based on the population pharmacokinetic analysis, age, sex, race, weight, mild or moderate hepatic impairment and mild, moderate, or severe renal impairment do not have a

clinically meaningful effect on venetoclax clearance.

Special patient populations: Venetoclax should not be administered to pregnant women. It is not known whether venetoclax is excreted in human milk, so venetoclax should not be administered to nursing mothers.

Hepatic Impairment: Mean venetoclax AUC exposures in subjects with severe hepatic impairment were approximately 2.3- to 2.7-fold higher as compared with subjects with normal hepatic function. On the basis of these results, a dose adjustment in patients with severe hepatic impairment is recommended.

15.16 **Potential Drug Interactions:** Venetoclax is predominately metabolized by CYP3A4 in vitro, thus CYP3A4 inhibitors or inducers are expected to cause changes in venetoclax exposures. Venetoclax should not be used with strong CYP3A inhibitors (e.g., ketoconazole, ritonavir, clarithromycin, itraconazole, voriconazole) at initiation and during ramp-up phase. Concomitant use of venetoclax with moderate CYP3A inhibitors (e.g., erythromycin, ciprofloxacin, diltiazem, fluconazole, verapamil), or strong CYP3A inducers (e.g., carbamazepine, phenytoin, rifampin, St. John's wort), or moderate CYP3A inducers (e.g., bosentan, efavirenz, etavirine) should be avoided. For patients who have completed the ramp-up phase and are on a steady daily dose of venetoclax, concomitant use of strong and moderate CYP3A inhibitors may be allowed with venetoclax dose reductions. If a strong CYP3A inhibitor must be used after the ramp-up phase, reduce the venetoclax dose by at least 75%. If a moderate CYP3A inhibitor must be used, reduce the venetoclax dose by at least 50%.

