Appendix I: Sample List of Excluded and Cautionary Medications for Patients treated with of polatuzumab vedotin, venetoclax, and rituximab and hyaluronidase human

Туре	Medication					
Excluded during the venetoclax ramp venetoclax	-up period and cautionary after patients are on 400 mg/day of					
Strong CYP3A inducers	Avasimibe, carbamazepine (Tegretol), phenobarbital, phenytoin (Dilantin), rifampin (Rifadin), and St. John's wort					
Moderate CYP3A inducers	Bosentan, efavirenz, etravirine, modafinil, and nafcillin					
Strong CYP3A inhibitors ^a	Boceprevir, clarithromycin, conivaptan, indinavir, itraconazole, ketoconazole, mibefradil, lopinavir/ritonavir, nefazodone, nelfinavir, ritonavir, posaconazole, saquinavir, telaprevir, telithromycin, and voriconazole					
Moderate CYP3A inhibitors ^a	Amprenavir, aprepitant, atazanavir, ciprofloxacin, crizotinib ^b , darunavir/ritonavir, diltiazem, erythromycin, fluconazole, fosamprenavir, imatinib ^b , and verapamil					
Cautionary throughout the study						
Warfarin						
Weak CYP3A inducers	Amprenavir, aprepitant, armodafinil, clobazamechinacea, pioglitazone, prednisone, rufinamide, and vemurafenib ^b					
Weak CYP3A inhibitors	Alprazolam, amiodarone, amlodipine, atorvastatin, bicalutamide ^b , cilostazol, cimetidine, cyclosporine ^b , fluoxetine, fluvoxamine, ginkgo, goldenseal, isoniazid, nilotinib ^b , oral contraceptives, pazopanib ^b , ranitidine, ranolazine, tipranavir/ritonavir, ticagrelor, and zileuton					
P-gp substrates	Aliskiren, ambrisentan, colchicine, dabigatran etexilate, digoxin, everolimus ^b , fexofenadine, lapatinib ^b , loperamide, maraviroc, nilotinib ^b , ranolazine, saxagliptin, sirolimus ^b , sitagliptin, talinolol, tolvaptan, and topotecan ^b					
BCRP substrates	Methotrexate ^b , mitoxantrone ^b , irrinotecan ^b , lapatinib ^b , rosuvastatin, sulfasalazine, and topotecan ^b					
OATP1B1/1B3 substrates	Atrasentan, atorvastatin, ezetimibe, fluvastatin, glyburide, rosuvastatin, simvastatin acid, pitavastatin, pravastatin, repaglinide, telmisartan, valsartan, and olmesartan					
P-gp inhibitors	Amiodarone, azithromycin, captopril, carvedilol, dronedarone, felodipine, quercetin, ronalzine, and ticagrelor					

Appendix II: Recommendations for Initial Management of Electrolyte Imbalances and Prevention of Tumor Lysis Syndrome

FIRST DOSE OF VENETOCLAX OR DOSE ESCALATION

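### Section 9.6 prohibits strong and moderate CYP3A agents and warfarin throughout the trial, but Appendix I makes them only cautionary (CYP3A agents once on 400 mg/day) and 15.16 allows inhibitors after ramp-up at a cut venetoclax dose

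*Combined protocol and SAP*

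**What the plan says.** **CYP3A agents.** Section 9.61, part of the list of prohibited therapies in 9.6, reads "Treatment with strong and moderate inhibitors or inducers of CYP3A is not allowed during this trial" and sends the reader to Appendix I for more information. It sets no phase limit. Appendix I puts strong and moderate inducers and inhibitors under one heading: excluded during ramp-up, and "cautionary after patients are on 400 mg/day of" venetoclax. The moderate-inducer row, for example, reads "Bosentan, efavirenz, etravirine, modafinil, and nafcillin".

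Section 15.16 treats the two directions differently. For inducers it says that strong ones, "or moderate CYP3A inducers (e.g., bosentan, efavirenz, etavirine) should be avoided". For inhibitors, once ramp-up is complete, "concomitant use of strong and moderate CYP3A inhibitors may be allowed with venetoclax dose reductions". It gives the cuts, in per cent: "If a strong CYP3A inhibitor must be used after the ramp-up phase, reduce the venetoclax dose by at least 75" and "If a moderate CYP3A inhibitor must be used, reduce the venetoclax dose by at least 50". Nursing guideline 15.192 tells staff not to combine venetoclax with strong inhibitors, with no time limit.

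**Warfarin.** Section 9.63 prohibits it, and exclusion 3.29i keeps out patients who require it. Appendix I lists it first under "Cautionary throughout the study". Sections 15.16 and 15.194 advise closer INR checks for patients who take it with venetoclax.

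**The concern.** A site that has to treat an infection or a clot in mid-trial gets a different answer depending on the page it opens. No clause says which text prevails. Section 9.61 itself directs the reader to the appendix that relaxes it.

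The situation is foreseeable. Section 15.17 names serious infection as a known risk of venetoclax, and 9.4 requires broad-spectrum antibiotics in some cases of severe diarrhea. Appendix I lists several anti-infectives in the affected classes: ciprofloxacin, fluconazole, posaconazole and voriconazole as inhibitors, rifampin and nafcillin as inducers.

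At stake are patient safety and consistent conduct across sites, including what counts as a protocol deviation. The statistical design is not at stake.

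**Working it through.** The plan states no figure to reproduce. The check sets the texts side by side, followed by short arithmetic for scale.

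| Agent | Section 9.6 | Appendix I | Section 15 | Result |
|---|---|---|---|---|
| Strong and moderate inducers | Prohibited, no phase limit (9.61) | Excluded in ramp-up, cautionary at 400 mg/day | To be avoided (15.16) | Firm conflict, 9.61 against Appendix I; 15.16 sides with 9.61 |
| Strong inhibitors | Prohibited, no phase limit (9.61) | As above, rows marked with footnote a | Allowed after ramp-up with a cut of at least 75% (15.16); not to be combined (15.192) | Firm conflict, 9.61 against 15.16 and the Appendix I heading; 15.192 also differs from 15.16 |
| Moderate inhibitors | Prohibited, no phase limit (9.61) | As above, rows marked with footnote a | Allowed after ramp-up with a cut of at least 50% (15.16) | Firm conflict, 9.61 against 15.16 and the Appendix I heading |
| Warfarin | Prohibited (9.63) | Cautionary throughout | INR advice only (15.16, 15.194) | Firm conflict, 9.63 against Appendix I |

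**The missing footnote.** The text of footnote a was not available for this check. It is attached only to the two inhibitor rows and may carry dose guidance like that in 15.16. Even then, the inhibitor rows would match 15.16 and still contradict 9.61. The inducer rows and the warfarin entry carry no mark a, so those conflicts hold whatever the footnote says.

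**Entry criteria.** Exclusion 3.29j covers CYP3A agents only in the 7 days before registration, and 3.29i concerns a need for warfarin at entry. Neither settles use on study.

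**Doses implied by 15.16, where 9.61 allows no combination.**
- From 400 mg: strong, 400 × (1 − 0.75) = 100 mg at most; moderate, 400 × (1 − 0.50) = 200 mg at most.
- From 300 mg, the de-escalated level in 7.61: strong, 300 × 0.25 = 75 mg; moderate, 300 × 0.50 = 150 mg. Tablets must not be broken (15.14) and the small strengths are 10, 50 and 100 mg (15.12). The largest whole-tablet dose not above 75 mg is therefore 50 + 10 + 10 = 70 mg; 150 mg is 100 + 50.

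**A gap at 300 mg.** The cautionary tier in Appendix I starts at 400 mg/day. For patients kept at 300 mg or lower it is not plain when, if ever, that tier applies.

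**How long the CYP3A texts differ in induction.** Induction is 6 × 21 = 126 days. Table 7.2b reaches 400 mg in week 5, after 4 × 7 = 28 days, so the texts differ on 126 − 28 = 98 days (98/126 = 78%). If ramp-up is counted as five full weeks, the figure is 126 − 35 = 91 days (91/126 = 72%). This assumes no delay or reduction and describes only the overlap of wording. The warfarin conflict has no ramp-up limit.

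**The case against.** The best defence is that the structure already gives the answer. Sections 9.61 and 9.63 stand under a heading of prohibited therapies. Section 15 is drug information. Appendix I calls itself a sample list. A cautionary entry is not permission, and patients who need warfarin are excluded at entry. The need for a listed drug is also partly conjecture: 9.4 names no antibiotic, and the planned prophylaxis in 7.1 (acyclovir, Bactrim) is not in Appendix I.

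Much of this stands as a limit on the harm, but none of it removes the conflict. A drug that is prohibited cannot also be merely cautionary. Section 15.16 gives operative dosing instructions. Section 15.199a refers vaccine questions to 9.6, but 15.192 and 15.194 carry no such pointer. Section 9.63 does not cite Appendix I, so the view that the appendix qualifies section 9 cannot reach warfarin.

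Three stronger readings are tempting, and the documents do not support them:

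- A reader might infer that the protocol lets a site give a strong inhibitor with full-dose venetoclax 400 mg. That depends on what footnote a says, and the site would also have to disregard 15.16 and 15.192.
- A reader might infer that 15.16 and 15.194 authorise warfarin. They are conditional monitoring advice. They presume co-administration and so sit badly with 9.63, but they do not grant it.
- A reader might take 78% or 72% of induction days as a measure of risk. These figures say how long two texts differ, not how many patients take such a drug.

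**Conclusion.** The inconsistency is real and should be corrected. It is firm in three places: 9.61 against Appendix I for inducers; 9.61 against 15.16 and the Appendix I heading for inhibitors; and 9.63 against Appendix I for warfarin. The inducer and warfarin conflicts do not depend on the missing footnote. For inducers, the difference between Appendix I and 15.16 is one of strength, cautionary against to be avoided; the outright contradiction is with 9.61.

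In dose terms, for a patient on 400 mg the instructions range from no inhibitor at all (9.61) to an inhibitor with venetoclax at most 100 mg or 200 mg (15.16). The documents do not say how many patients would need such a drug, so no frequency or harm can be estimated.

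A reader might also infer that the trial's result is affected. Nothing supports that: the sample size, the decision rule in 16.2 and the primary analysis in 16.31 do not depend on these texts. The documents do not settle whether the sponsor intends a full ban on inhibitors or the 15.16 allowance; that is a clinical choice the sponsor must state.

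**What to change.** 1. **Inducers and warfarin.** In Appendix I, list strong and moderate CYP3A inducers and warfarin as excluded throughout study treatment, in line with 9.61, 9.63 and 15.16. Replace the warfarin text in 15.16 and 15.194 with a pointer to 9.63.
2. **Inhibitors.** State one rule in 9.61 and make Appendix I, 15.16 and 15.192 refer to it. The default is exclusion throughout.
3. **If the sponsor keeps the 15.16 allowance** for an inhibitor that becomes medically unavoidable after ramp-up, write it into 9.61 and Appendix I:
   - From 400 mg: at most 100 mg of venetoclax with a strong inhibitor, 200 mg with a moderate one.
   - From 300 mg: at most 70 mg with whole tablets (strong) and 150 mg (moderate).
   - During induction, refer to the monitoring in 15.26, which predicts a 45% rise in unconjugated MMAE AUC when polatuzumab vedotin is given with ketoconazole.
   - Say that an interaction cut is not a dose reduction under Table 7.3 note 3. As worded, that note carries any induction reduction into maintenance, so a short course of an azole could fix the lower dose for the year.

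The cost is protocol wording in 9.61, 15.16, 15.192, 15.194 and Appendix I, plus one sentence at Table 7.3 note 3 if the allowance is kept. Sample size, visits and analyses do not change.

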9.62 Proton pump inhibitors

If subject is taking proton pump inhibitors, subject should be advised to avoid coadministration and stagger venetoclax dosing.

9.63 Treatment with warfarin is prohibited due to potential DDIs that may increase the exposure of warfarin.

9.64 Vaccination with a live virus vaccine is prohibited during this trial.

10.0 Adverse Event (AE) Reporting and Monitoring

The site principal investigator is responsible for reporting any/all adverse events to the sponsor as described within the protocol. Refer to the adverse event and serious adverse event sections of the protocol for detailed information.

The sponsor/sponsor-investigator is responsible for notifying FDA and all participating investigators in a written safety report of any of the following:

- Any suspected adverse reaction that is both serious and unexpected.
- Any findings from laboratory animal or *in vitro* testing that suggest a significant risk for human subjects, including reports of mutagenicity, teratogenicity, or carcinogenicity.
- Any findings from epidemiological studies, pooled analysis of multiple studies, or clinical studies, whether or not conducted under an IND and whether or not conducted by the sponsor, that suggest a significant risk in humans exposed to the drug.
- Any clinically important increase in the rate of a serious suspected adverse reaction over the rate stated in the protocol or Investigator's Brochure (IB).

Definitions

Adverse Event

Any untoward medical occurrence associated with the use of a drug in humans, whether or not considered drug related.

Suspected Adverse Reaction

Any adverse event for which there is a reasonable possibility that the drug caused the adverse event.

Expedited Reporting

Events reported to sponsor within 24 hours, 5 days or 10 days of study team becoming aware of the event.

Routine Reporting

Events reported to sponsor via case report forms

Events of Interest

Events that would not typically be considered to meet the criteria for expedited reporting, but that for a specific protocol are being reported via expedited means in order to facilitate the review of safety data (may be requested by the FDA or the sponsor).

10.1 Adverse Event Characteristics

CTCAE term (AE description) and grade: The descriptions and grading scales found in the revised NCI Common Terminology Criteria for Adverse Events (CTCAE) version 5.0 will be utilized for AE reporting. All appropriate treatment areas should have access to a copy of the CTCAE version 5.0. A copy of the CTCAE version 5.0 can be downloaded from the CTEP web site:

- a. Adverse event monitoring and reporting is a routine part of every clinical trial.
- b. Identify the grade and severity of the event using the CTCAE version 5.0.
- c. Determine whether the event is expected or unexpected (see Section 10.2).
- d. Determine if the adverse event is related to the study intervention (agent, treatment or procedure) (see Section 10.3).
- e. Determine whether the event must be reported as an expedited report. If yes, determine the timeframe/mechanism (see Section 10.4).
- f. Determine if other reporting is required (see Section 10.5).
- g. Note: All AEs reported via expedited mechanisms must also be reported via the routine data reporting mechanisms defined by the protocol (see Sections 10.53 and 18.0).

Each CTCAE term in the current version is a unique representation of a specific event used for medical documentation and scientific analysis and is a single MedDRA Lowest Level Term (LLT).

NOTE: A severe AE, as defined by the above grading scale, is NOT the same as serious AE which is defined in the table in Section 10.4.

10.2 Expected vs. Unexpected Events

Expected events - are those described within the Section 15.0 of the protocol, the study specific consent form, package insert (if applicable), and/or the investigator brochure, (if an investigator brochure is not required, otherwise described in the general investigational plan).

Unexpected adverse events or suspected adverse reactions are those not listed in Section 15.0 of the protocol, the study specific consent form, package insert (if applicable), or in the investigator brochure (or are not listed at the specificity or severity that has been observed); if an investigator brochure is not required or available, is not consistent with the risk information described in the general investigational plan.

Unexpected also refers to adverse events or suspected adverse reactions that are mentioned in the investigator brochure as occurring with a class of drugs but have not been observed with the drug under investigation.

10.3 Assessment of Attribution

When assessing whether an adverse event is related to a medical treatment or procedure, the following attribution categories are utilized:

Definite - The adverse event *is clearly related* to the agent(s).

Probable - The adverse event *is likely related* to the agent(s).

Possible - The adverse event *may be related* to the agent(s).

Unlikely - The adverse event *is doubtfully related* to the agent(s).

Unrelated - The adverse event is clearly NOT related to the agent(s).

Events determined to be possibly, probably or definitely attributed to a medical treatment suggest there is evidence to indicate a causal relationship between the drug/device and the adverse event.

10.31 EXPECTED Serious Adverse Events: Protocol Specific Exceptions to Expedited Reporting

For this protocol only, the following Adverse Events/Grades are expected to occur within this population and do not require Expedited Reporting. These events must still be reported via Routine Reporting (see Section 10.53).*

System Organ Class (SOC)	Adverse event/ Symptoms	CTCAE Grade at which the event will not be expeditedly reported.
General disorders and	Fatigue	≤Grade 3
administrations site conditions	Malaise	≤Grade 3
Blood and lymphatic	Febrile Neutropenia	≤Grade 3
system disorders	Neutrophil count decreased	≤Grade 3
	Thrombocytopenia	≤Grade 3
Investigations	Blood bilirubin increased	≤Grade 3
Metabolism and nutrition disorders	Tumor lysis syndrome	≤Grade 3

These exceptions only apply if the adverse event does not result in hospitalization. If the adverse event results in hospitalization, then the standard expedited adverse events reporting requirements must be followed.

The following hospitalizations are not considered to be SAEs because there is no "adverse event" (i.e., there is no untoward medical occurrence) associated with the hospitalization:

- Hospitalizations for respite care
- Hospitalization planned before informed consent (where the condition requiring the hospitalization has not changed post study drug administration)
- Hospitalization for administration of study drug or insertion of access for administration of study drug
- Hospitalization for routine maintenance of a device (e.g., battery replacement) that was in place before study entry
- *Report any clinically important increase in the **rate** of a serious suspected adverse reaction (at your study) site over that which is listed in the protocol or investigator brochure as an expedited event.
- *Report an expected event that is greater in severity or specificity than expected as an expedited event.
- *An investigational agent/intervention might exacerbate the expected AEs associated with a commercial agent. Therefore, if an expected AE (for the commercial agent) occurs with a higher degree of severity or specificity, expedited reporting is required.

A list of known/expected AEs is reported in the investigator brochure, package insert or the literature, including AEs resulting from a drug overdose

10.311 Death

- Any death occurring within 30 days of the last dose, regardless of attribution to an agent/intervention under an IND/IDE requires expedited reporting within 24-hours.
- Any death occurring greater than 30 days with an attribution of **possible, probable, or definite** to an agent/intervention under an IND/IDE requires expedited reporting within 24-hours.

Reportable categories of Death

- Death attributable to a CTCAE term.
- Death Neonatal: A disorder characterized by cessation of life during the first 28 days of life.
- Death NOS: A cessation of life that cannot be attributed to a CTCAE term associated with Grade 5.
- Sudden death NOS: A sudden (defined as instant or within one hour of the onset of symptoms) or an unobserved cessation of life that cannot be attributed to a CTCAE term associated with Grade 5.
- Death due to progressive disease that cannot be attributed to a
 CTCAE term associated with Grade 5 should be reported as
 Grade 5 "Disease progression" under the system organ class
 (SOC) of General Disorders and Administration Site Conditions.
 Evidence that the death was a manifestation of underlying
 disease (e.g., radiological changes suggesting tumor growth or
 progression: clinical deterioration associated with a disease
 process) should be submitted.

10.312 Secondary Malignancy

- A *secondary malignancy* is a cancer caused by treatment for a previous malignancy (e.g., treatment with investigational agent/intervention, radiation or chemotherapy). A secondary malignancy is not considered a metastasis of the initial neoplasm.
- All secondary malignancies that occur following treatment with an agent under an IND/IDE to be reported. Three options are available to describe the event:
 - Leukemia secondary to oncology chemotherapy (e.g., Acute Myeloctyic Leukemia [AML])
 - Myelodysplastic syndrome (MDS)
 - o Treatment-related secondary malignancy
- Any malignancy possibly related to cancer treatment (including AML/MDS) should also be reported via the routine reporting mechanisms outlined in each protocol.

10.313 Second Malignancy

 A second malignancy is one unrelated to the treatment of a prior malignancy (and is NOT ametastasis from the initial malignancy).
 Second malignancies require ONLY routine reporting.

10.314 Pregnancy

Prior to obtaining private information about a pregnant woman and her

infant, the investigator must obtain consent from the pregnant woman and the newborn infant's parent or legal guardian before any data collection can occur. A consent form will need to be submitted to the IRB for these subjects if a pregnancy occurs. If informed consent is not obtained, no information may be collected.

In cases of fetal death, miscarriage or abortion the mother is the patient. In cases where the child/fetus experiences a serious adverse event other than fetal death, the child/fetus is the patient.

NOTE: When submitting

the potential risk of

exposure of the fetus to the investigational agent(s) or chemotherapy agent(s) should be documented in the "Description of Event" section. Include any available medical documentation.

- **10.4** Expedited Adverse Event Reporting Requirements for IND/IDE Agents
 - 10.41 Phase 1 and Early Phase 2 Studies: Expedited Reporting via the **MedWatch form** for Adverse Events That Occur Within 30 Days¹ of the Last Dose of the Investigational Agent

FDA REPORTING REQUIREMENTS FOR SERIOUS ADVERSE EVENTS (21 CFR Part 312)

NOTE: Investigators MUST immediately report to the sponsor ANY Serious Adverse Events, whether or not they are considered related to the investigational agent(s)/intervention (21 CFR 312.64)

An adverse event is considered serious if it results in ANY of the following outcomes:

- 1) Death
- 2) A life-threatening adverse event
- 3) An adverse event that results in inpatient hospitalization or prolongation of existing hospitalization for ≥ 24 hours
- 4) A persistent or significant incapacity or substantial disruption of the ability to conduct normal life functions
- 5) A congenital anomaly/birth defect.
- 6) Important Medical Events (IME) that may not result in death, be life threatening, or require hospitalization may be considered serious when, based upon medical judgment, they may jeopardize the patient or subject and may require medical or surgical intervention to prevent one of the outcomes listed in this definition. (FDA, 21 CFR 312.32;ICH E2A and ICH E6).

ALL SERIOUS adverse events that meet the above criteria MUST be immediately reported to the sponsor within the timeframes detailed in the table below.

Hospitalization	Grade 1 and Grade 2 Timeframes	Grade 3-5 Timeframes
Resulting in Hospitalization ≥24 hrs	7 Calendar Days	24-Hour; 3 Calendar Days
Not resulting in Hospitalization ≥ 24 hrs	Not required	24-Hour, 3 Calendar Days

Expedited AE reporting timelines are defined as:

- o "24-Hour; 3 Calendar Days" The AE must initially be reported within 24 hours of learning of the AE, followed by a complete expedited report within 3 calendar days of the initial 24-hour report.
- o "7 Calendar Days" A complete expedited report on the AE must be submitted within 7 calendar days oflearning of the AE.

Serious adverse events that occur more than 30 days after the last administration of investigational agent/intervention and have an attribution of possible, probable, or definite require reporting as follows:

Expedited 24-hour notification followed by complete report within 3 calendar days for:

• All Grade 3, 4, and Grade 5 AEs

Expedited 7 calendar day reports for:

• Grade 2 AEs resulting in hospitalization or prolongation of hospitalization

² For studies using PET or SPECT IND agents, the AE reporting period is limited to 10 radioactive half-lives, rounded UP to the nearest whole day, after the agent/intervention was last administered. Footnote "1" above applies after this reporting period.

Effective Date: May 5, 2011

Special Instructions:

Follow site-specific reporting guidelines.

1) Submit SAE's using the MedWatch form 3500A.

or found on the ACCRU web site) along with the ACCRU Safety Reporting Cover Page (found on the ACCRU web site under Study Resources → Forms) to the ACCRU SAE Coordinator via email at

2) The ACCRU SAE Coordinator will forward to Genentech at

3) The ACCRU SAE Coordinator will forward to ACCRU IND Coordinator as appropriate. The ACCRU IND Coordinator will assist the sponsor-investigator in notifying the FDA if required.

- 4) ACCRU must be notified via email at following occurs:
- Data related to a suspected transmission of an infectious agent by the study drug (STIAMP), as defined below.

 Any organism, virus, or infectious particle (e.g., prion protein transmitting transmissible spongiform encephalopathy), pathogenic or non-pathogenic, is considered an infectious agent. A transmission of an infectious agent may be suspected from clinical symptoms or laboratory findings that indicate an infection in a patient exposed to a medicinal product. This term applies only when a contamination of the study drug is suspected.
- This event will require expedited reporting and will be treated like a serious adverse event with regard to reporting timeframes.

Genentech Adverse Events of Special Interest (AESI): AEs of Special Interest are defined by Genentech as a potential safety problem identified as a result of ongoing safety monitoring of their products. As such, surveillance for the AESIs below MUST be undertaken at each treatment evaluation. The following events are events of special interest and will require expedited reporting AT ANY GRADE and will be treated like a serious adverse event with regard to reporting timeframes.

Events of clinical interest for this trial include:

Potential drug-induced liver injury (DILI) as defined by Hy's Law

- a. Investigations
 - i. Alanine aminotransferase increase
 - ii. Aspartate aminotransferase increase

- b. Metabolism and nutritional disorders
 - i. Tumor Lysis Syndrome
- c. Secondary Malignancies
 - i. Treatment related secondary malignancy

Adverse Event	Needed		ACCRU timeline to report to sponsor
Non-Serious Adverse Event (Sections 10.52- 10.53)	Adverse Events form (see CRF packet)	At each evaluation	Quarterly
Adverse Events of Special Interest (Section	Adverse Events of Special Interest Form**	At each occurrence	Within 1 business day of receipt
10.41 special instructions)	Adverse Events form (if criteria in 10.5 is met)		Quarterly
Pregnancy (Section 10.314)	MedWatch Form**	At each occurrence	Within 1 business day of receipt
Serious Adverse Events (Section 10.41)*	MedWatch Form**	At each occurrence	Within 1 business day of receipt
10.41)	Adverse Events form (see CRF packet)		Quarterly

^{*}If an adverse event meets the criteria for both an AE of Special Interest and a Serious Adverse Event, please report only as a Serious Adverse Event.

